8 Follow up is conducted by telephone, unless the subject has an ongoing AE that requires physical examination or investigations for assessment/management. Visit 8 will take place 14 days after Visit 4 (week 12/Early Termination) unless subject discontinued treatment early and end of study/Week 52 assessments occurred 14 days or more after the last dose.

9 Visit Windows: Maximum of 14 days between screening and randomization. Subjects randomized to IV Iron must complete Visit 2 ideally on the day of randomisation or within 5 days. The subject must visit to complete:

Visits 3 and 4: +/- 1 week relative to date of Visit 2/first dose administered

Visit 4 to 7: +/- 1 week relative to date of Visit 2/first dose administered

Visit 8: 14 days (+5 days) after Visit 4 (unless subject discontinued treatment early and end of study/Week 12 assessments occurred 14 days or more after the last dose).

10 SF36 to be administered at Week 0 (baseline), and Week 12, 24, 36, and 52.

11 SF36 is not collected at this visit.

- 12 For CD subjects, a CDAI diary card will be provided at Screening, for completion over the 7 days prior to scheduled Visit 2. The screening haematocrit value will be used for the screening CDAI calculation to assess eligibility prior to randomization and will also count as the baseline CDAI value. For CD subjects, CDAI diary cards will then be provided at Visits 3 and 4. Subjects who went beyond week 12 will receive CDAI diary at Visit 5 and 6 for completion over the 7 days prior to the scheduled dates of Visit 4, 5, 6 and 7.
- 13 Retained serum and plasma samples will only be collected from trial subjects at those Investigator sites who have suitable freezer facilities for storage of the samples at -70°C/-80°C, prior to subsequent periodic shipping to the central laboratory on dry-ice. Detailed instructions will be provided in the Laboratory Manual.
14. Dispense/Administer study drug: based on the randomization stratification subjects will receive FCM/Ferric Maltol on Visit 2. If subjects went beyond Visit 4 (Week 12) and their treatment period will be continuing according to previous protocol until the next scheduled visit.
15. Visit 5 (Week 24) will only occur if subjects went beyond Visit 4 according to previous protocol, otherwise this will be the End of Study Visit.
16. Visit 6 (Week 36) will only occur if subjects went beyond Visit 5 (week 24) according to previous protocol, otherwise this will be the End of Study Visit.

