6.5 Multiple Comparisons and Multiplicity

There are no planned adjustments for multiple comparisons.

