9.2 Secondary Efficacy Analyses

9.2.1 Secondary Analysis

9.2.1.1 Key Secondary Endpoints

The change from baseline (CFB) in Hb concentration at Week 12 (MI) secondary endpoint will be analysed for the ITT population using an analysis of covariance (ANCOVA) model.

For the multiple imputation, the code for implementing the SAS® procedure MIANALYZE to the CFB Hb concentration at Week 12 secondary endpoint is:

```
DATA CFB_Impute; SET MI_out; CFBHbW12 = Week12Hb - baselineHb; RUN;
```

```
PROC SORT DATA = CFB_Impute; BY _Imputation_; RUN;
```

```
PROC REG DATA = CFB_Impute OUTEST = outreg COVOUT;  
  BY _Imputation_;  
  MODEL CFBHbW12 = binarybaselineHb TreatmentArm IBDGroup;  
RUN;
```

```
PROC MIANALYZE DATA = outreg EDF = <complete-data degrees of freedom>;  
  MODELEFFECTS Intercept binarybaselineHb TreatmentArm IBDGroup;  
  ODS OUTPUT ParameterEstimates = parm1;  
RUN;
```

The ANCOVA model will have terms for treatment arm, baseline Hb (below the observed median or at least the observed median), and IBD subgroup. The treatment effect of ferric maltol compared to IV Iron will be considered using differences of adjusted means. No formal statistical significance level in the treatment comparison will be defined, as the p-value from the ANCOVA model will be presented for descriptive purposes only. A summary of CFB in Hb concentration (OC) will be provided using descriptive statistics for each visit over the Treatment Period by treatment arm and overall. The summary will include the following

ANCOVA model estimates: adjusted means (i.e., Least-Square Means [LSMs]) of CFB in Hb concentration at Week 12 for each treatment arm, the difference in treatment arm LSMs, the corresponding 95% CIs for treatment arm specific LSMs and difference in treatment arm LSMs, and the p-value for the difference in treatment arm LSMs. Mean CFB in Hb concentration will be plotted against visit (OC) by treatment arm for the ITT and PP populations.

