The latter transformation is carried out such that each scale is mapped to the scale of the 1998 general United States (US) population [4]. The two summary scores, MCS and PCS, are computed by aggregating norm-based component scores using factor score coefficients from the 1990 general US population [4]. The aggregated summary scores are standardized to have a mean of 50 with a standard deviation of 10, in the general 1998 US population [4]. The full SF-36 scoring algorithm is published in [4] and is the approach we take here to score the SF-36. A summary of each of the 8 subscales and the 2 summary scores will be presented using descriptive statistics by visit (OC) for each treatment arm and overall.

The change from baseline (CFB) in each of the 8 SF-36 component subscales and the 2 summary scores will be calculated for each visit during the Treatment Period (BOCF) and analysed with separate ANCOVA models. Each ANCOVA model will include terms for treatment arm, baseline Hb (below the observed median or at least the observed median), and IBD subgroup. A hypothesis test for the treatment effect of ferric maltol compared to IV Iron will be conducted using differences of adjusted means. Statistical significance in the treatment comparison will be declared if the p-value of the hypothesis test from the ANCOVA model is less than or equal to 0.05. Significance levels will not be adjusted for multiplicity. A summary of CFB in each SF-36 subscale and each summary score will be provided using descriptive statistics for each visit during the Treatment Period (OC and BOCF) by treatment arm. The summary will include the ANCOVA estimates: adjusted means (LSMs) of CFB in each SF-36 component and summary score for each treatment arm, the difference in treatment arm LSMs, corresponding 95% CIs for LSMs and difference in treatment arm LSMs, and the p-value for the comparison of treatment arm LSMs. Normality and homogeneity of variances for the residuals of each ANCOVA model will be assessed using the procedure outlined in [Section 9.2.1.1](#).

A data listing of the SF-36 questionnaire will be presented by visit and subject.

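### SAP v3.0 section 10.1 lets significance be declared at an unadjusted 0.05 for each of 10 SF-36 scores at each collection visit, while the p-value for change in Hb, a key secondary endpoint, is descriptive only

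*SAP*

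**What the plan says.** Section 10.1 of SAP v3.0 defines the outcomes: "The change from baseline (CFB) in each of the 8 SF-36 component subscales and the 2 summary scores will be calculated for each visit" of the Treatment Period. Each score has its own ANCOVA and its own hypothesis test of ferric maltol against IV iron. The decision rule follows: "Statistical significance in the treatment comparison will be declared if the p-value of the hypothesis test from the ANCOVA model is" at or below the 0.05 level. On adjustment, the section then adds: "Significance levels will not be adjusted for multiplicity". This agrees with the general rule in section 6.5: "There are no planned adjustments for multiple comparisons".

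The footnotes to Table 1 fix the visits: "SF36 to be administered at Week 0 (baseline), and Week 12, 24, 36, and 52". Week 4 is excluded: "SF36 is not collected at this visit".

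For change in Hb to Week 12, which section 2.3.2 lists as a key secondary endpoint, section 9.2.1.1 takes the opposite line: "No formal statistical significance level in the treatment comparison will be defined, as the p-value from the ANCOVA model will be presented for descriptive purposes". Section 9.2.1.2 says the same of the CIs and p-values for the Hb rise responder endpoints.

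The later post-hoc SAP does not touch the SF-36 rule. Its section 10 refers the pharmacoeconomic analyses back to v3.0.

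**The concern.** Section 10.1 does more than report p-values. It says when a difference will be called statistically significant, and it gives that permission separately to every score at every visit. It names no lead score, lead visit or testing order, and it does not label the results exploratory. Section 6.1 treats every analysis in the plan as defined in advance and keeps the exploratory label for analyses added after database lock. An isolated subscale result could therefore be reported as a pre-specified significant finding for either arm.

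The plan is also uneven. An ANCOVA of the same form on a higher-ranked endpoint, change in Hb, is denied any significance level. The SF-36 sits among the pharmacoeconomic measures (section 2.3.3), and section 14 says it was not explicitly mentioned in the protocol as one of them. What is at stake is how quality-of-life results may be described in the CSR.

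**Working it through.** **Inputs**
- Scores: 8 + 2 = 10 (section 10.1).
- Post-baseline visits with SF-36: Weeks 12, 24, 36 and 52, so 4 (Table 1, footnotes 10 and 11).
- Tests: 10 × 1 = 10 at Week 12; 10 × 4 = 40 over all visits. After Week 12, only subjects enrolled before amendment 7.0 can contribute (sections 3.1 and 3.2.2).
- Level: 0.05 two-sided per test (sections 6.6 and 10.1).
- Correlations between test statistics: not in the document. I assume 0 to 0.8 between scores and 0 to 0.7 between visits.

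The plan states no family-wise error rate for the SF-36, so it has no figure of its own to reproduce.

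**Independent tests.** With no true difference on any score, P(at least one declared) = 1 − 0.95^k.
- k = 10: 1 − 0.95^10 = 0.401
- k = 40: 1 − 0.95^40 = 0.871

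The expected number of false declarations is 0.05 × k whatever the correlation: 0.5 for 10 tests and 2.0 for 40.

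Independence cannot hold here. The two summary scores are built from the same 8 subscales, and the visits repeat on the same subjects. For jointly normal statistics with two-sided limits, correlation can only lower the probability (Šidák's inequality), so 0.401 and 0.871 are upper limits.

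**One common correlation r.** With c = 1.96,

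P = 1 − ∫ φ(u) [Φ((c − √r·u)/√(1−r)) − Φ((−c − √r·u)/√(1−r))]^k du

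| r | 10 tests (Week 12) | 40 tests (all visits) |
|---|---|---|
| 0 | 0.40 | 0.87 |
| 0.3 | 0.35 | 0.75 |
| 0.5 | 0.29 | 0.57 |
| 0.7 | 0.21 | 0.38 |
| 0.8 | 0.17 | 0.28 |

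**Separate correlations between scores and between visits.** A 10 × 4 structure, simulated with 200,000 draws, gives for the 40 tests:

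| Between scores | Between visits | P |
|---|---|---|
| 0.3 | 0.5 | 0.76 |
| 0.5 | 0.5 | 0.67 |
| 0.7 | 0.5 | 0.54 |
| 0.7 | 0.7 | 0.47 |
| 0.8 | 0.7 | 0.39 |

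These lie inside the 0.28 to 0.87 range. The low end of that range requires scores at different visits to be as closely related as scores at the same visit.

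**The case against.** The strongest reply is disclosure. The plan says twice that it does not adjust (sections 6.5 and 10.1) and never claims to control error over the SF-36 family, so a reader can discount an isolated result. The SF-36 is a pharmacoeconomic endpoint and the non-inferiority decision does not depend on it. All of this stands, and it limits the weight of the point. It does not remove it: disclosing that levels are unadjusted does not justify calling each result significant.

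Four stronger readings are tempting, and the document does not support them.

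- A reader might infer that a false declaration is likely. At Week 12 alone the chance is below one half at every assumed correlation. For all 40 tests it falls below one half when correlation is high, and that count needs later visits that only part of the trial reaches.
- A reader might infer that the SF-36 alone is formally tested without control. It has the only explicit declaring sentence, but other tests are also unadjusted. Section 9.2.1.1 repeats the primary hypothesis testing for Hb normalisation, which sections 7.1.2 and 9.2.1.2 also call key. Section 9.2.1.3 extends that testing to anaemia status at Visits 5 to 7. Section 9.2.1.2 gives a significance p-value for ferritin, and section 10.2 tests repeat blood tests and transport.
- A reader might divide these probabilities by 0.05 and call the result an excess over the plan's stated level. The plan's 0.05 applies per test, so the two quantities are not comparable.
- A reader might argue that an open-label trial with self-reported outcomes needs multiplicity control all the more. Unblinded self-report raises a risk of bias, and adjusting significance levels does not cure bias.

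**Conclusion.** The point holds as a narrow one. Section 10.1 permits unadjusted declarations of significance over 10 SF-36 scores at up to four visits, with nothing to rank them, while change in Hb and the Hb rise responders receive descriptive p-values only. If no score truly differs between arms, the chance of at least one declared difference is about 17% to 40% at Week 12 and about 28% to 87% over all 40 tests. Both ranges rest on assumed correlations from 0.8 to 0. The upper ends are limits that the data cannot be expected to reach, and the 40-test figures count visits attended only by subjects enrolled before amendment 7.0. The primary non-inferiority conclusion is unaffected. The change should be made, but nothing in the main result depends on it.

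**What to change.** In section 10.1, replace the sentence that declares significance at 0.05 with the approach already taken in sections 9.2.1.1 and 9.2.1.2: no formal significance level is defined, and p-values and CIs are descriptive. Label the SF-36 results the same way in the CSR; version 2, announced in section 11 of the post-hoc SAP, is the natural place. No reanalysis is needed.

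The cost is one sentence of wording, and the sponsor can no longer call an isolated SF-36 result statistically significant.

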10.2 Correction and Maintenance of IDA

Status (yes or no) of administration of IV Iron will be documented at each visit (scheduled or unscheduled) over the Treatment Period for subjects randomized to the IV Iron treatment arm, commencing with the assessment conducted post-randomization at Visit 2. The total number of visits (scheduled and unscheduled) of administration of IV Iron over the Treatment Period will be calculated for each subject randomized to the IV Iron treatment arm. A summary of administration of IV Iron will be provided using descriptive statistics by visit, including a visit labelled "unscheduled", over all visits, and over Post-Day 0 visits. The summaries over all visits and Post-Day 0 visits will capture the respective number of hospital visits for administration of IV Iron and restart of IV Iron pharmacoeconomic endpoints. Missing values of administration of IV Iron will be kept as missing in the summary. A data listing of dose administration will be provided by subject.

Details of IV Iron dosing at the study site include: the duration of time (hours) spent at the study site for IV Iron administration; the dose (mg) of IV Iron

administered at the study site; and, the number of days off work (or, school/education or childcare) that the subject is required to miss due to administration of IV Iron at the study site, will be documented at each visit (scheduled or unscheduled) over the Treatment Period for subjects randomized to the IV Iron treatment arm. A summary of these IV Iron dosing details will be provided using descriptive statistics by visit (including a visit labelled "unscheduled"). A data listing of IV Iron dosing details will be provided by subject.

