2.1.2 Secondary Objectives

The secondary objectives of this study are:

- To evaluate the safety and tolerability of ferric maltol and intravenous iron (IVI, FCM) in subjects over a treatment duration of up to 52 weeks.
- To evaluate long-term healthcare resources utilized in the management of IDA in IBD.

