2.3.3 Pharmacoeconomic Endpoints

Pharmacoeconomic measures include the following:

- Number of hospital or clinic visits for administration of IV Iron.
- Proportion of subjects who restart IV iron during the study.
- Quality of life as assessed by the Medical Outcomes Study 36-item short form questionnaire.
- Correction and Maintenance of IDA
 - Repeat Hb or iron testing
 - Method of transportation to attend each visit.
 - The number of days off work or school/education to attend hospital or clinic visits for administration of IV Iron.
 - The time spent in the hospital or clinic receiving IV Iron.
 - The total dose of IV Iron administered over the study period.

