3.2.3 Follow-up Period (Visit 8)

At the end of the Treatment Period, subjects will enter a 14-day Follow-up Period during which AEs and concomitant medications will be monitored. At the end of the 14-day Follow-up Period, subjects will have their Follow-up visit (Visit 8). Visit 8 will be conducted by telephone interview, unless the subject has an ongoing AE that requires physical examination or investigations for assessment/management. If an AE is reported or is ongoing at the time of the Follow-up visit, or if a significant lab abnormality is identified at the last visit prior to the Follow-up visit, the Investigator must follow the event until resolution or until there is a satisfactory

explanation of the changes observed.

Table 1. Schedule of Assessments

	Screening	Treatment						⁸ Follow-up
Duration	Up to 14 days	Week						14 days
		0	4	12	(24) ¹⁵	(36) ¹⁶	(52) ¹⁷	(54)
⁹ Visits	1	2	3	4	(5)	(6)	(7)	(8)
Informed Consent	X							
Eligibility	X	X						
Demographics	X							
Medical history	X							
Physical examination	X							
¹ Vital signs	X							
² Height and weight	X	X	X	X	(X)	(X)	(X)	
³ Basic chemistry	X							
⁴ Liver function tests	X							
⁵ Haematology; Iron Markers	X	X	X	X	(X)	(X)	(X)	
C-reactive protein		X						
¹³ Retained plasma and serum samples		X		X				
⁶ Randomization		X						
Collect IV Iron History/IV Iron dosing detail	X	X	X	X	(X)	(X)	(X)	
SCCAI or CDAI ¹²	X ¹²			X	(X)	(X)	(X)	
¹⁰ Collect pharmacoeconomic (PE) and SF36 data		X	X ¹¹	X	(X)	(X)	(X)	
⁷ Pregnancy test	X			X			(X)	
Dispense/Administer study medication ¹⁴		X		(X)	(X)	(X)		
Compliance check			X	X	(X)	(X)	(X)	
Adverse events		X	X	X	(X)	(X)	(X)	X
Prior/Concomitant medication	X	X	X	X	(X)	(X)	(X)	X

1 Vital signs (blood pressure & heart rate) are taken after subject has been sitting for 5 minutes.

2 Height & weight measured during Screening, weight only at other visits.

3 Basic chemistry: bicarbonate, BUN, creatinine, chloride, glucose, potassium, sodium, Vitamin B12 and folate, creatinine clearance (US-only).

4 Liver function tests: ALT, AST and total bilirubin.

5 Haematology and Iron markers all visits: haematocrit, haemoglobin, platelets, RBC count, RBC Hb concentration; WBC count and differential; total serum iron; ferritin, transferrin; TSAT.

6 Maximum 14 days between Screening and randomization.

7 Urine pregnancy test, kits provided by central laboratory.

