9 EFFICACY ANALYSES

9.1 Primary Efficacy Analyses

9.1.1 Primary Analysis

Haemoglobin (Hb) concentration will be summarised at screening (Visit 1), pre-randomization at Visit 2 (baseline assessment), and at each visit over the Treatment Period. Hb concentration (Observed Cases [OC]) will be summarised for the ITT (post hoc table 14.2.1.1) and re-evaluated PP (post hoc table 14.2.1.2) populations using descriptive statistics by visit for each treatment arm and overall. A scatterplot of Hb concentrations (OC) at each visit versus baseline will be presented by treatment arm for the re-evaluated PP population (post hoc figures 14.2.1.4, 14.2.1.5.1, 14.2.1.5.2, 14.2.1.6, 14.2.1.8, 14.2.1.10, 14.2.1.12.1, 14.2.1.12.2).

A dichotomous variable, representing response status in the degree to which Hb increases relative to baseline, will be calculated for each visit over the Treatment Period. Those subjects with at least 2g/dL increase in Hb from baseline or who

have normalization of Hb from baseline (≥ 12.0 g/dL for women, ≥ 13.0 g/dL for men) will be classified as "Hb responders". [*Post-hoc change from > 12.0 g/dL for women or > 13.0 g/dL for men*]. A shift from baseline of anaemic to non-anaemic status (ie Hb concentration shift from below to within the normal limits will be classified as "Hb normal limit responders". [*Post-hoc change to align Hb normal limit responder definition with the definition given in section 2*]. Patients who are normal at baseline cannot be classified as a responder. Ferric maltol patients who take IV Iron cannot be classified as responders after the intake of IV iron.

The null hypothesis for the primary efficacy endpoint analysis is that the proportion of Hb responders at Week 12 in the ferric maltol treatment arm is at least 20% lower than the proportion of Hb responders at Week 12 in the IV Iron treatment arm (i.e., ferric maltol is inferior to IV Iron for rate of Hb response at Week 12). The alternative hypothesis is that the proportion of Hb responders at Week 12 in the ferric maltol treatment arm is not worse than 20% lower than the proportion of Hb responders at Week 12 in the IV Iron treatment arm (i.e., ferric maltol is non-inferior to IV Iron for rate of Hb response at Week 12).

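### Section 10.2 summarises IV iron visits, dose, site hours and days off only for the IV iron arm, so IV iron given to ferric maltol subjects is left out of endpoints defined without an arm restriction

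*SAP*

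**What the plan says.** SAP v3.0, Section 10.2, fixes who is counted. On visits it states: "The total number of visits (scheduled and unscheduled) of administration of IV Iron over the Treatment Period will be calculated for each subject randomized to" intravenous iron. Hours on site, mg given and days off "will be documented at each visit (scheduled or unscheduled) over the Treatment Period for subjects randomized to the IV Iron treatment arm. A summary of" such details follows, again descriptive and by visit. The section then links these displays to the endpoints: "The summaries over all visits and Post-Day 0 visits will capture the respective number of hospital visits for administration of IV Iron and restart of" intravenous treatment.

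Other parts of the document are wider:

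- Section 2.1.2 sets the secondary objective "To evaluate long-term healthcare resources utilized in the management of IDA in IBD".
- Section 2.3.3 lists "Number of hospital or clinic visits for administration of IV Iron" and "Proportion of subjects who restart IV iron during the study", and then days off, time on site and total dose, with no arm named in any of them.
- Section 10 makes ITT the default for pharmacoeconomic displays unless noted otherwise. Section 16.1 labels Tables 14.2.9.1 and 14.2.9.2 as ITT.
- Table 1 has a row "Collect IV Iron History/IV Iron dosing detail", marked from screening to Week 52 with no arm limit.
- The post-hoc SAP, Section 9.1.1, adds the rule "Ferric maltol patients who take IV Iron cannot be classified as responders after the intake of IV iron". Its Section 10 plots time to first additional or rescue IV iron, and otherwise refers back to v3.0 for the pharmacoeconomic analyses.

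**The concern.** The plan treats IV iron taken by a ferric maltol subject as an event that matters for efficacy, since it rules out response from then on. The same event enters none of the Section 10.2 summaries of visits, mg, hours or days off.

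The objective is about resources used to manage the anaemia. For an oral treatment set against an infusion, a natural use of these tables is to ask how many infusions and clinic visits the oral arm was spared. That reading needs the infusions the oral arm did receive. Leaving them out shifts the answer in one direction only, and by more the more often oral treatment had to be supplemented.

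**Working it through.** The SAP states no figure for IV iron resource use, so there is none to reproduce. The check is mainly a comparison of the text, followed by an illustration of scale.

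**1. Who is counted.** Section 10.2 limits administration status, number of visits, hours, mg and days off to subjects randomised to IV iron. The limit is explicit for each item.

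**2. Whom the endpoint covers.** Section 2.3.3 names no arm and the table titles say ITT, which Section 5.3 defines as all randomised subjects. A programmer who follows 10.2 produces a table that its title does not describe.

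**3. Whether the excluded event can occur.** Post-hoc SAP 9.1.1 says so directly for ferric maltol patients. Post-hoc Section 10 refers to rescue IV iron without naming an arm, and SAP v3.0 Section 5.3 refers to IV iron outside the protocolled dose, also without an arm. None gives a frequency.

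**4. Whether another display recovers it.**

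| Display | What it shows | What it lacks |
|---|---|---|
| Concomitant medications (8.6, Table 14.3.3.2) | Recorded IV iron by generic name and arm | Visits, hours, days off |
| Kaplan-Meier plot (post-hoc Section 10) | Time to first additional or rescue IV iron from Visit 4 | Anything before Visit 4, subjects consented under amendment 7, visits, mg, hours, days off |
| Table 14.2.12 (post-hoc) | Total IV iron in 52-week completers | Ferric maltol arm |

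None supplies the missing resource use.

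**5. Whether a planned contrast is affected.** For these items 10.2 plans descriptive statistics and listings only. The two resource analyses that do compare arms, repeat Hb or iron tests and method of transport, count both arms.

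**6. Scale, by assumption only.** Let r be the share of ferric maltol subjects given IV iron, v their mean IV iron visits, and m the mean visits in the IV iron arm. The arm size is 121 (Section 4: 108 × 1.12 = 120.96, rounded to 121). The values of r, v and m are assumed, because the documents give none.

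- Visits omitted per ferric maltol subject = r × v
- Visits omitted in the arm = 121 × r × v
- Overstatement of the difference in mean visits, if a reader takes the untabulated arm as zero = m / (m − r × v) − 1

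| r | v | Omitted per subject | Omitted in arm | Overstatement, m = 2 | Overstatement, m = 4 |
|---|---|---|---|---|---|
| 0 | – | 0 | 0 | 0% | 0% |
| 0.05 | 1 | 0.05 | 6.05 | 2/1.95 − 1 = 2.6% | 4/3.95 − 1 = 1.3% |
| 0.20 | 2 | 0.40 | 48.4 | 2/1.60 − 1 = 25% | 4/3.60 − 1 = 11.1% |

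The m = 4 column is there because Section 3.2.2 allows further IV iron after Week 12 in the IV iron arm. Both arms must be counted over the same follow-up.

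**The case against.** The strongest reply is that no planned comparison is biased. A reader might infer from the one-arm rule that the trial's healthcare-resource comparison is tilted toward ferric maltol, but the SAP specifies no contrast, model, interval or test for these items. That reply stands.

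A reader might also infer that the plan assigns ferric maltol subjects zero IV iron. It does not. They are simply not tabulated, and missing values of IV iron administration stay missing. An absent column differs from a column of zeros. The zero arises only if someone reads it into the gap.

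Four further points carry weight:

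- The ITT default yields where the text notes otherwise, and 10.2 arguably does so. That leaves the table titles and the unrestricted wording of 2.3.3 unreconciled.
- Restarting IV iron most naturally describes subjects who already began it, so that endpoint may properly belong to the IV iron arm.
- Recorded IV iron in ferric maltol subjects remains visible in the concomitant-medication table, so its use is not hidden; only its resource burden is.
- Section 10.2 speaks of documenting hours and days off in the IV iron arm, so the restriction may lie in data collection. The Table 1 row does not prove that these details exist for ferric maltol subjects.

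These points narrow the concern. They do not explain why visits and mg, which dosing detail and concomitant medication may supply, should be summarised in one arm only.

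**Conclusion.** The point holds in limited form. Section 10.2 leaves IV iron given to ferric maltol subjects out of endpoints that Section 2.3.3 words for subjects generally and that the table titles label ITT. Any between-arm reading of the descriptive tables would understate ferric maltol resource use. The direction is certain, because omitted counts cannot be negative. The size is unknown and is zero if no ferric maltol subject received IV iron. The 1.3% to 25% in the non-zero rows above only illustrates assumed inputs and is not an estimate.

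The documents do not support the stronger statement that a specified resource comparison is biased. The primary and key secondary efficacy conclusions are untouched. This is a cheap improvement to descriptive displays that serve a secondary objective.

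**What to change.** In Section 10.2 and Tables 14.2.9.1 and 14.2.9.2:

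- Summarise IV iron administrations or visits, and mg, by randomised arm for all ITT subjects. Take them from IV iron dosing detail and concomitant medication, and count zero where none was given.
- Report hours on site and days off for ferric maltol subjects only where recorded, with the number of subjects contributing. If they were not collected in that arm, label those summaries as descriptive data for the IV iron arm.
- State whether the restart endpoint is meant for the IV iron arm alone, and align Section 2.3.3 and the table titles with the answer.

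The cost is SAP wording, one added column per table, and a derivation that draws on concomitant medication. The downside is incompleteness: hours, days off and possibly mg may be missing for ferric maltol subjects infused away from the study site, and the tables should say so.
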